7.2 Data Processing Rules

7.2.1 Handling of Missing Data

Missing observed values

Unless otherwise specified, all data will be based on the actual measurement data.

Missing dates

For incomplete date data, the dates in the listings will be presented according to the actual situation.

If the start date of any AE or prior/concomitant medication is missing, the following rules will be applied:

- If the start date is completely missing, it will be imputed with the first dose date of study drug. However, if the end date is not missing and occurs prior to the first dose of study drug, the start date will be replaced with the earliest of non-missing end date or informed consent date.
- If the start month and day are missing but the start year is available, the start date will be imputed with the first day (Day 1) of the first month (January). However, if the year is the same as that of the first dose of study drug, the start date will be the same as the date of the first dose of study drug.
- If the start day is missing but the start year and month are available, the start date will be imputed with the first day (Day 1) of the month. However, if the start year and month are the same as those of the first dose of study drug, the start date will be the same as the date of the first dose of study drug.

If the end date of any AE or prior/concomitant medication is missing, the following rules will be applied:

- For AE if the end date is completely missing, the end date will be the latest of the participant withdrawal/completion date, death date, last active day of study drug, or start date. For prior/concomitant medication with completely missing end date and is no longer administered, the end date will be imputed following above rule for AE with completely missing end date. Otherwise, the end date will not be imputed.
- If the end month and day are missing but the end year is available, the end date will be imputed with the last day of the last month (December). However, if the end year is the same as that of the completion/withdrawal date, the end date will be the same as the date of completion/withdrawal.
- If the end day is missing but the end year and month are available, the end date will be imputed with the last day of the month. However, if the end year and month are the same as those of completion/withdrawal, the end date will be the same as the date of completion/withdrawal.

These imputed dates will be used to determine whether an AE or medication occurs (is used) during treatment.

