##### **2) Target Population**

Participant has at least 1 year history of migraine (with or without aura) consistent with a diagnosis according to the International Classification of Headache Disorders, 3rd Edition, beta version, including the following:

- a) Age of onset of migraines prior to 50 years of age
- b) Migraine attacks, on average, lasting 4-72 hours if untreated
- c) 6-18 migraine attacks of moderate or severe intensity per month within the last 3 months prior to the Screening Visit

- d) Six or more migraine days requiring treatment during Observation Phase
- e) Ability to distinguish migraine attacks from tension/cluster headaches
- f) Participants on prophylactic migraine medication are permitted to remain on therapy if the dose has been stable dose for at least 2 months prior to the Baseline Visit, and the dose is not expected to change during the course of the study. Participants who previously discontinued prophylactic migraine medication must have done so at least 5 half-lives of the prophylactic medication prior to the Screening Visit
- g) Participants with contraindications for use of triptans may be included provided they meet all other study entry criteria

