7.3.6 Prior and Concomitant Medications

Summaries will be performed based on the SS.

Non-study drugs will be coded into Anatomical Therapeutic Chemical Classification System (ATC) codes and preferred drug names using the World Health Organization Drug Dictionary (WHO-DD). For multiple records of the same drug taken by a participant, the drug will be counted only once under each ATC Grade 2 term and/or PT item.

The non-study medication types include:

- Prior medications, including previous and current medications

Prior medications are defined as those taken before study drug, i.e., imputed start or end date < study drug start date. Note that all non-study medications are considered prior for participants with missing study drug start date. Prior medications include the

following subtypes:

- Previous medications, defined as those taken before informed consent, i.e., those with an imputed start or end date < informed consent date.
- Current medications, defined as those taken on or after informed consent and before study drug.
- Concomitant medications, defined as those taken with study drug.

Summaries will be provided for: current prophylactic migraine medications, concomitant prophylactic migraine medications, current medications, and concomitant medications, respectively.

All non-study previous, current, and concomitant medications, including prophylactic migraine medications and other medications, will be listed.

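### SAP 7.2.1 sets a wholly missing medication start date to first dose, so a drug already in use by then is left out of the current-medication summaries

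*SAP*

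**What the plan says.** SAP 7.2.1 opens its start-date rules with a joint scope: "If the start date of any AE or prior/concomitant medication is missing, the following rules will be applied". The parts that matter here are:

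- Start wholly missing: "If the start date is completely missing, it will be imputed with the first dose date of study drug".
- Exception: "if the end date is not missing and occurs prior to the first dose of study drug, the start date will be replaced with" the earlier of that end date and the consent date.
- Only the year known: 1 January of that year. However, "if the year is the same as that of the first dose of study drug, the start date will be the same as" the first-dose date. A parallel sentence does the same when year and month are known and match first dose.
- End date wholly missing for a medication that is still being taken: "Otherwise, the end date will not be imputed".

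The section then states what the dates are for: "These imputed dates will be used to determine whether an AE or medication occurs (is used) during treatment".

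SAP 7.3.6 classifies medications on those dates: "Prior medications are defined as those taken before study drug, i.e., imputed start or end date < study drug start date". *Current* is listed as a subtype of *prior* and covers drugs taken from consent up to study drug. Four summaries are planned: current prophylactic, concomitant prophylactic, current, and concomitant medications.

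Protocol 5.2, criterion 2f, says participants on prophylaxis are "permitted to remain on therapy if the dose has been stable dose for at least 2 months prior to the Baseline Visit". Protocol 5.5 repeats the condition.

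**The concern.** For an adverse event, moving an unknown onset to first dose is the cautious choice, because the event then counts as treatment-emergent. A background medication raises a different question: was the participant already taking it before study drug? The same rule answers no whenever the start is unknown and the drug has not ended before first dose.

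For a preventive the answer conflicts with the protocol. Study drug is dispensed at Baseline and taken after eligibility is confirmed, so first dose does not precede Baseline. A continuing preventive in an eligible participant began at least 2 months before Baseline, so a start on the first-dose date cannot be right.

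What is at stake is descriptive. The current prophylactic summary shows the background prevention that participants brought into a single-arm trial. Read beside the concomitant prophylactic summary, it shows whether that background was stable. The rule can lower the first count and leave the second unchanged.

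**Working it through.** The plan gives no figure on this point, so there is none to reproduce. The check applies the SAP 7.2.1 rules and the SAP 7.3.6 definitions literally to test records. The dates are assumed for illustration: consent 1 March 2023, first dose 5 April 2023.

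Definitions applied:

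- prior = (imputed start < first dose) or (end < first dose)
- current = prior, and still taken on or after consent
- concomitant = no end date, or end on or after first dose

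| Recorded start | Recorded end | Imputed start | Current | Concomitant |
|---|---|---|---|---|
| Known, 5 May 2020 (reference) | ongoing | 5 May 2020 | yes | yes |
| Wholly missing | ongoing | 5 April 2023 | **no** | yes |
| Wholly missing | 1 August 2023 | 5 April 2023 | **no** | yes |
| Wholly missing | on first-dose date | 5 April 2023 | **no** | yes |
| Wholly missing | 20 March 2023 | 1 March 2023 | yes | no |
| Wholly missing | 10 January 2023 | 10 January 2023 | no (previous only, correct) | no |
| 2020 only | ongoing | 1 January 2020 | yes | yes |
| 2023 only | ongoing | 5 April 2023 | **no** | yes |
| January 2023 | ongoing | 1 January 2023 | yes | yes |
| April 2023 | ongoing | 5 April 2023 | **no** | yes |

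Rows 1 and 2 can be the same drug in the same person. With the start known it is both current and concomitant; with the start unknown it is concomitant only. The reason is the strict inequality: 5 April 2023 < 5 April 2023 is false, and there is no earlier end date. Not prior implies not current.

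The same-year row can arise for an eligible preventive, for example one begun early in the year by a participant first dosed late in that year. The same-month row cannot, if the record is right, because of the 2-month condition. It can arise for other drugs.

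**Size.** The documents give neither the number of prophylaxis users nor the number of missing start dates. On the planned 240 participants, each one lost from a summary line lowers its percentage by 1/240 = 0.42 points. As an illustration only, assume that 20% use prophylaxis (0.20 × 240 = 48) and that a share f of them have an unknown start:

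- f = 0: none lost; the line reads 20.0%.
- f = 5%: 0.05 × 48 = 2.4 lost; (48 − 2.4)/240 = 19.0%.
- f = 20%: 0.20 × 48 = 9.6 lost; (48 − 9.6)/240 = 16.0%.

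Both assumed rates are outside the documents.

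**The case against.** The case for leaving the rule alone has real content.

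- **The rule is cautious for its stated purpose.** SAP 7.2.1 uses imputed dates to decide what was taken during treatment, and the rule keeps every uncertain ongoing drug in the concomitant summary. This stands. The cost is confined to the pre-dose summaries.
- **Most dated records are safe.** The exception for a recorded end before first dose covers triptans stopped before first dose, which Protocol 5.5 requires to be discontinued at Baseline. A partial date in an earlier year or month is also classified correctly. This stands too, so it would be wrong to say that long-standing migraine drugs in general are misclassified.
- **Missing starts may be rare.** Criterion 2f makes the site establish at least 2 months of stable dosing. Footnote 2 to the protocol's Table 1 has all concomitant medication recorded via BYOD and reviewed at each visit. Whether the CRF allows a blank start, or carries an ongoing-before-study flag, cannot be seen. Nothing in the documents shows that older drugs lack start dates more often.

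A reader might also infer that stable background prevention will be reported as prevention newly begun with rimegepant. The documents do not support that. SAP 7.3.6 plans participant counts by drug class and name, not a table of start dates or new starts, and SAP 7.2.1 has incomplete dates listed as collected. At most, someone comparing the two prophylactic summaries could misread the gap, and the listing would correct it.

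None of this removes the central point: for a drug in use at first dose with no start date, the written rule gives a class that cannot be right for an eligible preventive.

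**Conclusion.** The point holds in a narrow form and is minor. The rule misclassifies ongoing medications that have a wholly missing start date. It does the same to those in use before dosing whose partial start matches the year, or year and month, of first dose. They are undercounted in the current and current prophylactic summaries.

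The concomitant counts of drugs in use at first dose are correct. (A drug already stopped with both dates missing depends on the end-date rule and is not part of this point.) It would be tempting to extend the concern to the trial's results, but nothing supports that. No planned subgroup or model uses current-medication status. SAP 7.4.1 keeps all migraine-day values observed after standard-of-care medication, acute or prophylactic. The primary safety analyses do not use the medication classes.

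The number of affected records cannot be derived from the documents and may be small or zero. The conclusion rests on a literal reading of SAP 7.2.1 and 7.3.6 and on there being no overriding CRF flag, which the documents do not mention.

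**What to change.** Separate the medication rule from the adverse-event rule in SAP 7.2.1, and leave the adverse-event rule as it is.

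1. For a medication with a wholly missing start and no end date before first dose, treat it as started before informed consent, so that it counts as both current and concomitant, unless it is recorded as newly started on treatment.
2. For a prophylactic whose partial start falls in the same year or month as first dose, do not move it to the first-dose date when the record shows that it was in use before Baseline.

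A blanket rule that takes the earliest date consistent with every partial start is not advised. It could place a drug truly begun after dosing before first dose, or even before consent, and so exchange one error for another.

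The cost is a few SAP sentences and a small programming change; no endpoint is touched. The downside is that a few drugs truly begun after first dose, with no start date and no record of being new, would also count as current.

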### **8.1. Definition of Adverse Events**

According to the definition in GCP, an adverse event is any untoward medical occurrence in a clinical trial participant administered an investigational product that may present with symptoms/signs, disease, or laboratory abnormalities and which do not necessarily have a causal relationship with the investigational product.

In order to collect more sufficient information, following the participant's written consent to participate in the study, information on clinical adverse events will be collected in this study. Any clinical adverse event that occurs after signing the informed consent form and before the first use of the investigational product and meets one of the following conditions should be recorded as a pretreatment adverse event: injury/damage caused by any clinical laboratory test procedure; adverse event caused by drug discontinuation related to the trial protocol; adverse event caused by drugs other than the study product (or investigational product) taken as part of the treatment regimen. TEAEs are events that start after the first dose of trial drug and do not occur or worsen relative to the first dose.

Examples of an AE include:

1. Any abnormal laboratory test results (hematology, clinical chemistry, or urinalysis) or other safety assessments (e.g., ECGs, radiological scans, vital signs measurements), including those that worsen from baseline, and felt to be clinically significant in the medical and scientific judgement of the investigator.
2. Exacerbation of a chronic or intermittent pre-existing condition including either increase in frequency and/or intensity of the condition.
3. New conditions detected or diagnosed after study treatment administration even though it may have been present prior to the start of the study.
4. Signs, symptoms, or the clinical sequelae of a suspected drug-drug interaction.

Examples of NOT meeting definition of an AE include:

1. Any clinically significant abnormal laboratory findings or other abnormal safety assessments which are associated with the underlying disease. However, it was considered an AE if the investigator considered the intensity to be more severe than the expectation for the participant 's status.
2. The disease/disorder being studied or expected progression, signs, or symptoms of the disease/disorder being studied. However, it should be considered an AE when its severity exceeds the expected severity of the participant 's condition.

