7.2.4 Analysis Periods

To facilitate the analyses based on eDiary data (including eDiary compliance and migraine days), the analyses for safety endpoints, the following analysis periods will be defined.

Table 1. Analysis Periods

Analysis periods	Start date/time	End date/time	Usage
OP	Screening Visit date	LT _T start date – 1 day	To be used to calculate the eDiary compliance, number of migraine days per 4 weeks in this period.
LT _T	Earlier of (1) Baseline Visit date, and (2) study drug start date	Later of (1) Week 52/EOT date, and (2) study drug last dose date	To be used to calculate the eDiary compliance and number of migraine days per 4 weeks or the overall period in the long-term treatment.
Pre-treatment safety		Study drug start date – 1 day for AEs; study drug start date/time otherwise	To be used to assess the safety endpoints prior to study drug treatment.
Treatment safety	Study drug start date for AEs; after study drug start date/time otherwise	[Later of (1) Week 52/EOT date, and (2) study drug last dose date] + 7 days	To be used to assess the safety endpoints of the treatment period.
Follow-up safety	[Later of (1) Week 52/EOT date, and (2) study drug last dose date] + 8 days		To be used to assess the safety endpoints of the follow-up period.

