7.5.2 Adverse Events

The AEs will be coded by the latest version of MedDRA. The toxicity of AEs will be graded using National Cancer Institute Common Terminology for Adverse Events (NCI CTCAE) v5.0.

All AEs will be categorized according to the safety analysis periods (refer to Section 7.2.4), ie. pre-treatment safety period, treatment safety period, and follow-up safety period:

- Pre-treatment AEs, ie, those with imputed AE onset dates falling within the pre-treatment safety period.
- Treatment-emergent adverse event (TEAEs), ie, those with imputed AE onset dates falling within the treatment safety period. See Section 7.2.1 for AE onset date imputation.
- Follow-up AEs, i.e., those with imputed AE onset dates falling within the follow-up safety period.

Drug-related AEs are the AEs assessed by the site investigator as having a relationship to the investigational product of "definitely related", "probably related", or "possibly related".

An overall summary of AEs will display the number and percentage of participants reporting the following AEs for participants in different categories of average rimegepant exposure (< 2 , ≥ 2 to < 8 , ≥ 8 to < 14 , < 14 and ≥ 14 tablets per month) and overall participants for treatment safety and follow-up safety analysis periods, respectively, as below:

- For treatment safety analysis period, the following will be summarized using SS:
 - Any TEAE, any drug-related TEAE,
 - Any serious TEAE, any drug-related serious TEAE,
 - Any TEAE with CTCAE grade ≥ 3 , any drug-related TEAE with CTCAE grade ≥ 3 ,
 - Any TEAE leading to drug interruption; any drug-related TEAE leading to drug interruption,
 - Any TEAE leading to treatment discontinuation, any drug-related TEAE leading to treatment discontinuation,
 - Any TEAE leading to study discontinuation, any drug-related TEAE leading to study discontinuation,
 - Any TEAE leading to death, any drug-related TEAE leading to death.

- For follow-up safety analysis period, the following will be summarized using FUSS:
 - Any AE,
 - Any SAE,
 - Any AE leading to death.

Further, the number and percentage of participants with the following AEs will be tabulated by SOC and PT for participants in different categories of average rimegepant exposure (< 2 , ≥ 2 to < 8 , ≥ 8 to < 14 , < 14 and ≥ 14 tablets per month) and overall participants for treatment safety and follow-up safety analysis periods, respectively, as below:

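### SAP 7.2.1 books an adverse event that ended before first dose as a TEAE when its partial start date matches the first-dose year, or year and month

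*SAP*

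**What the plan says.** SAP 7.2.1 has three rules for an incomplete AE start date:

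- **Completely missing.** Impute the first-dose date. There is a guard: "However, if the end date is not missing and occurs prior to the first dose of study drug", the start becomes the earlier of the end date and the consent date.
- **Year only.** Impute 1 January, except that "if the year is the same as that of the first dose of study drug", the first-dose date is used.
- **Year and month.** Impute day 1 of the month, except that "if the start year and month are the same as those of the first dose of study drug", the first-dose date is used.

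The section closes by saying that "These imputed dates will be used to determine whether an AE or medication occurs (is used) during treatment". In SAP 7.2.4, Table 1 gives the start of the treatment safety period as "Study drug start date for AEs; after study drug start date/time otherwise". SAP 7.5.2 defines TEAEs as "those with imputed AE onset dates falling within the treatment safety period". Protocol 8.1 says that "TEAEs are events that start after the first dose of trial drug".

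**The concern.** The guard against a pre-dose end date stands in one branch of three. In the two matching exceptions, a recorded end date that settles the timing is ignored. The result is perverse: a record with no start date at all is classified correctly, while the same record with a known year or month is not.

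Nothing later in the SAP repairs this, because the TEAE definition uses imputed onset only. Medications are better protected: SAP 7.3.6 calls a medication prior if either its start or its end precedes study drug.

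AE incidence is the primary endpoint, and Protocol 10.5.2 bases its analysis mainly on TEAEs. A rule that counts events already over before any drug was taken inflates that incidence and creates records whose onset follows their end.

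**Working it through.** The plan gives no figure to reproduce. The check has three parts: follow the rules as written, measure how far they reach, and test the repair.

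**1. Worked example (hypothetical dates).** Consent 15 Feb 2023, first dose 20 Mar 2023 (33 days later), AE end 5 Mar 2023. An AE is a TEAE if imputed onset is on or after 20 Mar.

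| Recorded start | Onset under SAP 7.2.1 | Class | Onset with the repair |
|---|---|---|---|
| missing | 15 Feb 2023 | pre-treatment | unchanged |
| 2023 | 20 Mar 2023 | TEAE | 15 Feb 2023 |
| Mar 2023 | 20 Mar 2023 | TEAE | 1 Mar 2023 |
| Feb 2023 | 1 Feb 2023 | pre-treatment | unchanged |
| Jan 2023 | 1 Jan 2023 | pre-treatment | unchanged |
| 2022 | 1 Jan 2022 | pre-treatment | unchanged |

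In both TEAE rows, onset falls 15 days after the event ended, so duration (end − start + 1) is −14 days. Only the two matching exceptions fail. A partial end date can fail too: start 2023 with end Feb 2023 (imputed 28 Feb) also gives onset 20 Mar.

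**2. Reach of the rule.** This is conditional on a partial date and is not a count of records. Assume a gap of G days from consent to first dose, and take every start/end pair lying wholly between consent and the day before first dose, with equal weight.

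- An AE starting k days before dose has k possible end days, so there are G(G+1)/2 pairs per first-dose day. With G = 33 that is 33 × 34/2 = 561, and over the 365 first-dose days of 2023 it is 365 × 561 = 204,765.
- *Day missing.* The record is misbooked when the start falls in the first-dose month. For first dose on day d of the month this gives (d−1)d/2 pairs (valid when G is at least 30). Summed over a month, this is 4,960 for 31 days, 4,495 for 30 days and 3,654 for 28 days. The year total is 7 × 4,960 + 4 × 4,495 + 3,654 = 56,354, and 56,354/204,765 = 27.5%.
- *Year only.* The record is misbooked when the start falls in the first-dose year. The first 33 days of the year contribute 5,984 pairs (the sum of (j−1)j/2 for j = 1 to 33) and the other 332 days contribute 332 × 561 = 186,252. The total is 192,236, and 192,236/204,765 = 93.9%.

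| Assumed gap (days) | 28 | 30 | 33 | 40 | 45 | 60 |
|---|---|---|---|---|---|---|
| Day missing | 37.5% | 33.2% | 27.5% | 18.8% | 14.9% | 8.4% |
| Year only | 94.8% | 94.4% | 93.9% | 92.6% | 91.7% | 88.9% |

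The weighting matters. A separate run with a two-day AE and a 32-day gap gave 43% for day missing and 95% for year only.

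**3. Test of the repair.** Over the same pairs with complete end dates, at all six gaps:

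- no AE that ended before dosing remained a TEAE;
- no imputed start fell after its end or contradicted the recorded year or month in the matching branches;
- no non-matching record changed;
- no record with an end date on or after first dose, or with no end date, changed.

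**4. Effect per participant.** One affected participant with no other TEAE adds 1/240 = 0.42 percentage points to any-TEAE incidence.

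**The case against.** The strongest reply is that very few records can be affected.

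- **Small pool.** Protocol 8.1 says that a pre-dose event which "meets one of the following conditions should be recorded as a pretreatment adverse event" and then lists only three kinds. It also sends pre-existing complaints unrelated to the study intervention to medical history. Against that, Protocol 8.5 and footnote 7 of the Schedule of Activities collect AEs from consent, so the pool is narrowed but not empty.
- **Several conditions must coincide.** The start date must stay partial after queries (Protocol 11.2.2), match the first-dose year or month, and come with an end date before dosing. Sites ask about AEs at Screening, during the Observation Period and at Baseline, so recall is short. A year-only start is especially unlikely in such a window.
- **Limited harm.** The error only adds TEAEs. Drug-related counts are largely spared because investigators weigh timing (Protocol 8.9). SAP section 5 plans no formal test. Listings show dates as recorded and flag each AE's period, so a careful reader could spot the conflict.
- **The percentages rest on an arbitrary weighting.** That is true; they describe the rule, not the expected data.
- **The Protocol 8.1 TEAE sentence is garbled in its second half and silent on partial dates.** That is also true, but its requirement that onset follow first dose is clear.

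These points limit the size of the effect. None makes the rule correct for a date that stays partial. Defaulting to first dose is a sensible conservative choice when timing is unknown, but here the recorded end date makes it known.

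**Conclusion.** The concern holds. Applied exactly as written, SAP 7.2.1 classifies an AE recorded as finished before first dose as a TEAE in the two matching exceptions, against Protocol 8.1 and against the guard in the SAP's own completely-missing branch.

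The number of such records is not stated and is probably very small. The bias is always upward, at 0.42 percentage points of any-TEAE incidence per affected participant with no other TEAE (denominator 240, the planned enrolment), and it falls mainly on all-causality counts. The conclusion about the rule needs no assumption. The reach percentages depend on the assumed gap and on the weighting of pairs. Because this is a primary-endpoint classification rule and the correction is nearly free, it should be changed.

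**What to change.** In the two matching exceptions of SAP 7.2.1, add a condition for AEs. If the end date is known to precede first dose (a complete date, or a partial date whose last possible day is before first dose), set onset to the later of the consent date and the first day of the known year or month, and never after the end date.

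Do not copy the completely-missing rule literally. With a recorded start of Mar 2023 in the example it would give 15 Feb, contradicting the recorded month. Leave the non-matching branches (1 January, or day 1 of the month) as they are.

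The cost is one clause applied in two places and trivial programming. It uses AE start and end dates and the consent date, all already collected.
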